7.9.2 Missing Items on Rating Scales

Missing values for post-baseline assessments will be imputed by the last observed value immediately prior to the missing value carried forward (LOCF). This rule does not apply to individual items in a multiple-item assessment. LOCF is used after imputation, ie, LOCF values are not used for calculations of subscale/scale scores.

The general rule when individual items are missing from a multiple-item assessment is as follows: the total score will be calculated using a SAS function CEIL, as $\text{CEIL}[(\text{sum of nonmissing items}) \times (\text{total number of items}) / (\text{number of nonmissing items})]$. If more than 20% of the items are missing, the total score will be set to missing. The implications of this rule are indicated in [Table 7.c](#) for each rating scale. The resulting calculated total scores will be used in all analyses.

Table 7.c Number of Missing Items on Rating Scales Associated with a Missing Value

CONFIDENTIAL

for Total Score

Parameter	Number of Missing Items
CSFQ-14	≥ 3
CSFQ _i or CSFQ dimension or CSFQ 3-phases	≥ 1

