9.1.8 Sexual Functioning Assessments

9.1.8.1 *CSFQ-14*

The CSFQ-14 is a structured self-reported questionnaire designed to measure illness- and medication-related changes in sexual functioning that consists of 14 items measuring sexual functioning as a total score (14 items) and on the subscales of pleasure (1 item), desire/frequency (2 items), desire/interest (3 items), arousal (3 items), and orgasm (3 items). Two additional items are included in the total score, but do not map to a specific phase of the sexual response cycle. Lower scores are associated with worsened sexual functioning [20]. The subject should complete the CSFQ-14 scale before the PGI-I scale at all post-baseline visits.

9.1.8.2 *PGI-I Scale*

The PGI-I scale is a global self assessment used to rate the response of a subject's condition to therapy or intervention. It consists of one question that asks the subject to rate their current condition compared to how it was prior to beginning treatment on a scale of 1 (very much better) to 7 (very much worse). It was originally developed for assessment in women with stress urinary incontinence [21]. However, due to its lack of specificity for medical conditions, and its sensitivity to change, it has been used for subject self assessment in other conditions. The subject should complete the CSFQ-14 scale before the PGI-I scale at all post-baseline visits.

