6.0 DETERMINATION OF SAMPLE SIZE

Approximately 352 male and female subjects will be randomized to 4 treatment arms. Randomization will be stratified by sex. Men and women will be enrolled in approximately equal proportions (ie, 50% men and 50% women overall).

Assuming an SD of 8.5 for the change from Baseline in CSFQ-14 total score, a total of 352 male and female subjects (88 subjects per arm) is sufficient to achieve $\geq 80\%$ power to detect a difference of 4.0 for vortioxetine 20 mg vs paroxetine 20 mg or for vortioxetine 10 mg vs paroxetine 20 mg by a 2-sample t-test with a 0.025 2-sided significance level. Given the proposed Holm-Bonferroni method (see Section 7.9.3) for multiplicity control, the power to achieve the significance for each vortioxetine dose is approximately 85%.

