7.9.1 Overview of Primary, Secondary and Additional Variables

The primary, secondary and additional variables for this study are presented in [Table 7](#).

Table 7.b Primary, Secondary and Additional Variables

Parameter	Description	Variable Type (a)
CSFQ-14	CSFQ-14 total score	1
PGI-I	PGI improvement	2
Sexual dysfunction (abnormal) assessed by CSFQ-14	CSFQ-14 total score ≤ 47 for men or ≤ 41 for women	3
Time to sexual dysfunction	Time to CSFQ-14 total score ≤ 47 for men or ≤ 41 for women	4
C-SSRS	Columbia-Suicide Severity Rating Scale	2
CSFQ _i	CSFQ-14 single item i	2
CSFQ 5-dimensions: Pleasure	CSFQ-14 item 1	2
CSFQ 5-dimensions: Desire/Frequency	Sum of CSFQ-14 items 2 and 3	1
CSFQ 5-dimensions: Desire/Interest	Sum of CSFQ-14 items 4, 5, and 6	1
CSFQ 5-dimensions: Arousal/Erection	Sum of CSFQ-14 items 7, 8, and 9	1
CSFQ 5-dimensions: Orgasm/Ejaculation	Sum of CSFQ-14 items 11, 12, and 13	1
CSFQ 3-phases: Desire	Sum of CSFQ-14 items 2, 3, 4, 5, and 6	1
CSFQ 3-phases: Arousal	Sum of CSFQ-14 items 7, 8, and 9	1
CSFQ 3-phases: Orgasm/Completion	Sum of CSFQ-14 items 11, 12, and 13	1
Δ CSFQ ≤ -3	CSFQ negative response (≥ 3 decrease from baseline)	3
Time to Δ CSFQ ≤ -3	Time to CSFQ negative response	4

(a) 1 = continuous; 2 = categorical; 3 = binary; 4 = time to event.

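### SAP 7.9.2 always rounds prorated CSFQ-14 totals up, shifting them by 0.46 or 0.42 points on average and adding negative responders when Baseline is prorated (minor)

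*SAP*

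**What the plan says.** SAP 7.9.2 sets one rule for multi-item scales. With k items answered out of 14 and a sum of S over those items, the total is CEIL(14S/k): "the total score will be calculated using a SAS function CEIL". The limit is "If more than 20% of the items are missing, the total score will be set to missing", and Table 7.c turns this into three or more missing items for the CSFQ-14 total. Single items, dimensions and phases are set to missing as soon as one item is missing, so they are never prorated. The rule therefore acts only on totals with one or two missing items.

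The scope is wide: "The resulting calculated total scores will be used in all analyses". Nothing limits the item rule to post-baseline visits, so it covers Baseline as well. Protocol 9.1.8.1 gives the direction of the scale: "Lower scores are associated with worsened sexual functioning". SAP Table 7.b defines a fall of 3 points or more from Baseline as a negative response. SAP 7.9.5 analyses that flag at all visits and also as a time to event.

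Neither document gives a reason for CEIL, an expected rate of missing items or a sensitivity analysis for the rounding. The protocol has no missing-item rule.

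**The concern.** CEIL never rounds down, so its error has one sign and does not average out over the prorated totals in an arm. A prorated post-baseline total understates worsening. A prorated Baseline overstates it, and does so at all five later visits. Baseline is also the covariate in the primary ANCOVA.

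The negative-response flag is the most exposed endpoint, because a threshold on whole points can be crossed by rounding alone.

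The main analyses do not need the rounding. ANCOVA and MMRM accept non-integer values. Because 47 and 41 are integers, a prorated total and its CEIL value always fall on the same side of those cut-offs.

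**Working it through.** **Inputs.** 14 items (Protocol 9.1.8.1); CEIL and the 20% limit (SAP 7.9.2); the 3-point threshold (SAP Table 7.b); SD 8.5, difference 4.0 and 88 per arm (SAP 6.0). Item scores are assumed to be integers.

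**1. The plan's own figure.** 2/14 = 14.3% is within the limit and 3/14 = 21.4% exceeds it. Three or more missing items is reproduced.

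**2. Size of the upward shift.**
- One missing: 14S/13 = S + S/13. The excess added by CEIL is one of 0, 1/13, ..., 12/13. With remainders evenly spread, the mean is 6/13 = 0.46 and the maximum 12/13 = 0.92. It is zero in 1 case in 13.
- Two missing: 14S/12 = S + S/6. The excess is one of 0, 1/6, ..., 5/6. The mean is 2.5/6 = 0.42 and the maximum 5/6 = 0.83. It is zero in 1 case in 6.
- With normally distributed scores (assumed means 45 to 55, SDs 5 to 8.5), the means are 0.44 to 0.48 and 0.42.

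**3. Negative response, Baseline prorated and later form complete.** For an integer later score P, CEIL(B) − P ≥ 3 exactly when B − P > 2. Every prorated fall strictly between 2 and 3 is therefore counted: 2.08 to 2.92 with one item missing, 2.17 to 2.83 with two.
- Example: 13 Baseline items sum to 53. Then 53 × 14/13 = 57.08, and CEIL gives 58. A later score of 55 is a fall of 3 (counted) instead of 2.08.
- With a complete Baseline and a prorated later form, CEIL never changes the flag.
- When both are prorated, CEIL can add a negative response relative to the unrounded scores but cannot remove one.

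**4. Leaving the score unrounded for this flag.** Take 13 Baseline items summing to 51: 51 × 14/13 = 54.92. Against a later 52, the unrounded fall is 2.92 and is not counted, although the nearest whole total, 55, gives a fall of 3. A simulation of 1,000,000 records measured the two errors. Its assumptions are not in the documents: exchangeable items scored 1 to 5, a complete later form, mean fall 2, SD 6. The true negative-response rate was 46.6%.

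| Baseline items missing | CEIL | Unrounded | Nearest integer |
|---|---|---|---|
| 1 | 49.7% | 43.7% | 46.7% |
| 2 | 49.4% | 44.0% | within 1 point of the true rate, depending on how halves are rounded |

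These errors apply only to subjects with a prorated Baseline. If 5% of an arm were such subjects (assumption), CEIL would raise that arm's rate by about 0.05 × (49.7 − 46.6) = 0.16 percentage points.

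**5. Primary contrast.** The shift in the raw difference at Week 5 is the between-arm difference in proration × 6/13. For assumed differences of 1, 5, 10 and 20 percentage points it is 0.005, 0.02, 0.05 and 0.09 points. The standard error of a difference is 8.5 × √(2/88) = 1.28, so the 10-point case is about 4% of one standard error and about 1% of the 4.0 design difference.

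**6. Cut-offs.** CEIL and the unrounded total agree at 47 and 41 for every possible sum. Nearest-integer rounding does not: 44 × 14/13 = 47.38 would round to 47 and be classed as dysfunction in a man.

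**The case against.** The strongest reply is that no treatment comparison is shown to be affected. Baseline forms are completed before the first dose in a randomized, double-blind trial. Baseline proration, the main route to reclassification, therefore cannot depend systematically on treatment. The rule is prespecified and the same in all arms. Negative response is only an additional endpoint, with no multiplicity control. All of this stands, and it is why the point is minor.

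A second reply is that simply deleting CEIL would reverse the negative-response error rather than remove it. That is correct, and the fix below allows for it.

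A third is that proration assumes exchangeable items, which a scale covering pleasure, desire, arousal and orgasm may not satisfy, and that its own error is larger than the rounding. That is fair, but rounding upward adds a one-signed error on top and corrects nothing.

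Integer totals do match complete forms and the display precision in SAP 7.1.2. That is a reason for tidy listings, not for rounding only upward.

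A reader might also infer three stronger things that the documents do not support:
- that every prorated total is inflated by nearly half a point, when 0.46 and 0.42 are averages and some totals do not move;
- that a prorated fall of exactly 2 points becomes a negative response, when the smallest fall reclassified is 2.08;
- that CEIL favours one arm on the primary endpoint, which would need a difference in proration between arms that nothing in the protocol or SAP suggests.

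**Conclusion.** The point holds as a minor one. CEIL puts an avoidable upward error into prorated values of the primary variable: 0.46 points on average with one item missing (0 to 0.92) and 0.42 with two (0 to 0.83). With a prorated Baseline and a complete later form, it lowers the negative-response threshold from a fall of at least 3 to any prorated fall above 2.

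The primary conclusion is not at risk: about 0.05 points even with a 10-percentage-point difference in proration between arms. The sizes of the shift rest on integer item scores and evenly spread remainders. The simulated rates rest on the assumptions stated with them. The total effect depends on a proration rate that the documents do not give. The dysfunction and entry classifications are unaffected.

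**What to change.** In SAP 7.9.2, before unblinding, replace CEIL for CSFQ-14 totals with one or two missing items:

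- Use the unrounded prorated total, 14S/k, for the ANCOVA and MMRM analyses, both as outcome and as Baseline covariate.
- Apply the 47 and 41 cut-offs to the same unrounded total. Every classification stays as it is under CEIL.
- For the 3-point negative-response flag and the time to it, use the prorated total rounded to the nearest integer, at Baseline and at later visits. State how halves are handled. They arise only with two items missing, and rounding them up leaves a mean shift of +0.08.
- Leave the 20% limit and Table 7.c unchanged.

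The cost is a short edit to one section and one extra derived variable. A few totals in the listings will not be whole numbers.

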7.9.3 Primary Efficacy Endpoint(s)

Mean change from Baseline in the CSFQ-14 total score difference for vortioxetine vs paroxetine after 5 weeks of treatment will be the primary endpoint. The primary analysis will be based on analysis of covariance (ANCOVA) using the last observation carried forward (LOCF) technique, with treatment, center, and sex as fixed factors, and baseline CSFQ-14 total score as covariate. The comparisons will be between each vortioxetine dose (10 or 20 mg) and paroxetine, and both statistical tests will be 2-sided.

The following example SAS code will be used for the ANCOVA analysis:

```
Proc mixed data=all;
  - class treat center sex;
  - model Change= Baseline treat center sex;
  - lsmeans treat;
```

In the above model, Baseline is the baseline value and Change is the change from baseline value.

The Holm-Bonferroni method will be used to adjust for multiplicity and control the familywise type I error rate at a significance level of 0.05. If the smaller of the 2 P-values is <0.025 , significance is obtained for the associated vortioxetine dose and the other dose will then be evaluated at a 0.05 significance level. Although vortioxetine will be compared with paroxetine in the primary analysis, paroxetine will also be compared with placebo to validate the study. The primary analyses will also be repeated based on the PPS if more than 5% of the total subjects in the FAS have major protocol violations.

As supportive analyses, the sex-by-treatment interaction term will be added to the primary analysis model to further check the sex effect on the treatment. The similar ANCOVA analyses will also be performed using the observed case (OC) data.

Change from Baseline in the CSFQ-14 total score will also be analyzed based on a mixed model for repeated measurements (MMRM) with treatment, center, week, treatment-by-week interaction and sex, as fixed effects, and baseline CSFQ-14 total score, and CSFQ-14 total score-by-week as covariates. The effect at each time point for each treatment is allowed to vary freely and an unstructured covariance matrix is assumed.

The SAS code for the MMRM analysis will be as follows:

```
Proc mixed data=all;
  - class week treat center subject;
  - model Change = baseline*week baseline treat center week week*treat sex /solution;
  - repeated week/subject=subject type=UN;
  - lsmeans week*treat / cl pdiff.
```

The potential influence of covariates on the primary efficacy analyses will be investigated in ANCOVA model by adding main terms for the covariate as well as interaction terms with treatment. Among the covariates to be investigated are sex, pooled center, race, baseline weight, BMI, and age.

For the primary efficacy variable (using both MMRM and ANCOVA), subgroup analyses by:

- age (\leq median, $>$ median).
- sex (female, male).
- race (Caucasian, Non-Caucasian).
- baseline CSFQ-14 total score (\leq median, $>$ median).

and other variables will be performed if each of the subgroups contains at least 20% of the total subjects in the study.

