6.2 Justification for Study Design, Dose, and Endpoints

6.2.1 Study Design

Healthy adult subjects were chosen for inclusion in this study to eliminate the confounding effects on sexual function associated with psychiatric conditions and certain medical conditions. The duration of 5 weeks was selected to allow for sufficient time to evaluate the extent of sexual dysfunction.

Paroxetine was chosen as an active comparator as it is a commonly prescribed SSRI and is known to cause sexual dysfunction, thereby allowing for validation of the study (ie, the level of sexual dysfunction with paroxetine is worse than that of placebo). The level of sexual dysfunction with vortioxetine 10 and 20 mg will also be compared with placebo.

Since study drug compliance is known to impact the study results, a compliance technology vendor, AiCure, will be used to throughout the study to improve study drug compliance. In addition, PK samples will be taken at 3 postbaseline study visits in order to assess plasma concentrations of vortioxetine and paroxetine. The compliance technology and/or PK concentration data will be used to define one or more modified full analysis set populations.

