7.5 Procedures for Discontinuation or Withdrawal of a Subject

The investigator may discontinue a subject's study participation at any time during the study when the subject meets the study termination criteria described in Section [7.4](#). In addition, a subject may discontinue his or her participation without giving a reason at any time during the study. Should a subject's participation be discontinued, the primary criterion for termination must be recorded by the investigator. In addition, efforts should be made to perform all procedures scheduled for the ET Visit. Discontinued or withdrawn subjects will not be replaced. Discontinued or withdrawn subjects will receive a Follow-up Contact.

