13.1.3 Efficacy Analysis

13.1.3.1 Primary Analysis

Mean change from Baseline in the CSFQ-14 total score difference for vortioxetine vs paroxetine after 5 weeks of treatment will be the primary endpoint. The primary analysis will be based on analysis of covariance (ANCOVA) using the last observation carried forward (LOCF) technique, with treatment, center, and sex as fixed factors, and baseline CSFQ-14 total score as covariate. The comparisons will be between each vortioxetine dose (10 or 20 mg) and paroxetine, and both statistical tests will be 2-sided. The Holm-Bonferroni method will be used to adjust for multiplicity and control the familywise type I error rate at a significance level of 0.05. If the smaller of the 2 p-values is <0.025 , significance is obtained for the associated vortioxetine dose and the other dose will then be evaluated at a 0.05 significance level. Although vortioxetine will be compared with paroxetine in the primary analysis, paroxetine will also be compared with placebo to validate the study.

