7.1.2 Summary Statistics and Precision

All tabulations of analysis results will include summaries for the following treatment groups: , vortioxetine 10mg/day, vortioxetine 20mg/day, paroxetine 20 mg/day and placebo.

All confidence intervals, statistical tests, and resulting p-values will be reported as nominal 2-sided and will be assessed at the 5% significance level. No adjustments will be made for multiplicity aside from those for the primary efficacy analysis.

For continuous variables, descriptive statistics will include the number of subjects (n), mean, SD or standard error (SE), as appropriate, minimum, median, and maximum. The number of decimal places displayed for each statistic will be determined as follows:

- Mean and median: 1 more than the number of decimal places allotted in the electronic case report form (eCRF) except for the CGI scales, where 2 decimal places will be reported.
- SD and SE: 2 more than the number of decimal places allotted in the eCRF.
- Minimum and maximum: equal to the number of decimal places allotted in the eCRF.
- Confidence intervals will be presented using the same number of decimal places as the parameters (eg, mean).

For categorical data, frequency counts and percentages will be presented. Percentages will be reported to 1 decimal place.

The data summaries will be accompanied by individual subject data listings sorted by treatment, study center and subject identifier. All data available from eCRFs will be listed. The actual day relative to the start of treatment will be determined and included in the listings.

Derived analysis datasets will be produced from raw data and laboratory data. This allows for convenient reviewing of the data as well as any necessary supplemental analyses. All data from the raw datasets will be included in the derived datasets. Derived dataset specifications will be developed to include the names and definitions of derived variables in the derived SAS datasets.

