7.1.3 Definition of Study Day and Study Visit Windows

A windowing convention will be used to determine the analysis value for a given study visit that applies to observed data.

Study Day -1 corresponds to the date of the Baseline visit, ie, the randomization date. Other study days are defined relative to Study Day 1, the date of first double-blind study drug dose. Relative day is calculated as (date of interest – date of first dose +1) for study days on or after the

date of first dose and as (date of interest – date of first dose) for study days prior to the first dose date.

For each visit, a window will be defined such that the lower and upper bounds of each window is generally the midpoint between 2 consecutive study visits. The visit windows and applicable study day ranges are presented below in [Table 7.a](#).

Table 7.a Visit Windows

Nominal Visit Week	Nominal Visit Day	CSFQ-14, PGI-I, C-SSRS	Vital signs	Lab, PE,Weight,	PK
Baseline	-1 (a)	≤1 (b)	≤1	≤1	≤1 (b)
1	7	2 – 10			
2	14	11 – 17	2-24		
3	21	18 – 24			2-24
4	28	25 – 31			25-31
5	35	≥32	≥25	≥2	≥32
7	49				

(a) Baseline day has been defined as Day -1 in keeping with Clinical Data Interchange Consortium standards. There is no Day 0.

(b) No baseline assessment for PGI-I or pharmacokinetic (PK) sampling.

More than 1 result for a parameter may be obtained in a visit window. In such an event, the result with the date closest to the scheduled visit day will be used. In the event of 2 observations equidistant to the scheduled visit day, the later of the observations will be used. Treatment Period Last Visit values will be defined irrespective of falling in a particular window. Hence, the windowed Week 8 value may be different than the Last Visit value.

In general, the baseline value for a variable is defined as the last observation prior to the first dose of double-blind study medication (visit date \leq first dose date), including the screening value, if necessary.

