7.3 Analysis Sets

The safety set will include all subjects who were randomized and received at least 1 dose of double-blind study medication. In safety summaries, subjects will be analyzed according to the treatment they received. In the event that a subject receives more than 1 treatment, the actual treatment will be defined as the 1 that is used most frequently. If the 2 most common treatments are used with equal frequency, then the randomized treatment will be used as the actual treatment.

The full analysis set (FAS) will include all subjects who were randomized, received at least 1 dose of study drug, and had at least 1 valid post-baseline value for assessment of primary efficacy. In FAS efficacy summaries, subjects will be analyzed by the treatment to which they were randomized.

To adjust for treatment noncompliance, two modified FAS populations, mFAS1 and mFAS2, will be defined based on the PK data. The mFAS1 excludes subjects in the vortioxetine treatment

CONFIDENTIAL

arm who had drug concentration below the limit of quantification at all study visits where PK is collected, while the mFAS2 excludes subjects in the vortioxetine treatment arm who had drug concentration below the limit of quantification at any study visit where PK is collected. The PPS will include all FAS subjects who had no major protocol violations. If more than 5% of the total subjects in the FAS have major protocol violations, analyses based on the PPS will be performed for the primary efficacy variable only.

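### The only multiplicity-controlled Week 5 tests use LOCF, so early leavers are tested on a Week 1-4 score, while the SAP's own MMRM carries no alpha

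*SAP*

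**What the plan says.** The primary endpoint is the vortioxetine-paroxetine difference in CSFQ-14 change at the end of treatment. Protocol 6.2.1 explains the length: "The duration of 5 weeks was selected to allow for sufficient time to evaluate the extent of sexual dysfunction".

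Protocol 13.1.3.1 specifies ANCOVA "using the last observation carried forward (LOCF) technique, with treatment, center, and sex as fixed factors", and SAP 7.9.3 agrees: "The primary analysis will be based on analysis of covariance (ANCOVA) using the last observation carried forward (LOCF) technique". Holm-Bonferroni covers the two dose-versus-paroxetine tests from that model. On everything else, SAP 7.1.2 is explicit: "No adjustments will be made for multiplicity aside from those for the primary efficacy analysis".

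Three SAP rules decide which score is tested:
- **Windows (7.1.3, Table 7.a).** Days 2-31 belong to Weeks 1-4, and Week 5 starts at Day 32. Efficacy data taken more than 7 days after the last dose are excluded.
- **Imputation (7.9.2).** A missing post-baseline visit takes the last observed value. A total score with 3 or more missing items is itself missing.
- **Analysis set (7.3).** A randomized, dosed subject enters the FAS if he or she "had at least 1 valid post-baseline value for assessment of primary efficacy".

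For leavers, Protocol 7.5 says that "efforts should be made to perform all procedures scheduled for the ET Visit". Appendix A exempts those who withdraw consent and refuse contact. Leavers are not replaced.

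SAP 7.9.3 also specifies an MMRM with unstructured covariance and treatment-by-week terms, and a supportive observed-case ANCOVA. Neither is assigned alpha, and SAP 7.9.4 calls MMRM a sensitivity method.

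**The concern.** The trial runs 5 weeks so that the effect has time to appear, but the test that decides the claim can use a score from any week. A subject whose last usable score is at Week 1 counts fully in the Week 5 comparison. In the vortioxetine 20 mg arm, that Week 1 score comes from the week at 10 mg/day (SAP 4.4). An early-termination visit does not close the gap: if it falls before Day 32, its score is itself a Week 1-4 score.

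LOCF gives the Week 5 difference only if leavers' scores would not have moved after they left. Nothing in the documents argues for that. If LOCF and MMRM disagree, LOCF decides by default, because only LOCF carries alpha. The plan has no missing-not-at-random analysis to show how much the answer depends on either assumption.

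**Working it through.** **1. The plan's own figures reproduce.** Inputs from SAP 6.0: difference 4.0, SD 8.5, 88 per arm, two-sided 0.025.
- SE = 8.5 x sqrt(2/88) = 1.28.
- Power of the two-sample t-test is 80.4% (noncentral t, 174 df), or 81.1% by the normal approximation. The plan says at least 80%.
- Holm power per dose, with both doses at 4.0 and a shared paroxetine arm, is 85.2% by simulation. The plan says about 85%.
- Both figures use 88 evaluable subjects per arm, with no allowance for dropout.

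**2. Which score is tested.** The Week 5 visit is Day 35 ± 3 from Baseline (Day 0). With the first dose on Day 1, that is SAP Days 32-38, so the Day 32 boundary fits the schedule. A subject with nothing usable from Day 32 on is carried forward from Days 2-31.

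**3. Closed form.** Assumptions: dropout unrelated to scores, last visits spread evenly over Weeks 1-4, Week 5 means of -2 (vortioxetine) and -6 (paroxetine). Let dv and dp be the dropout proportions in the two arms.
- Gradual onset (25/50/75/90/100% of effect): leavers carry (0.25 + 0.50 + 0.75 + 0.90)/4 = 0.60. LOCF difference = -2(1 - 0.4dv) + 6(1 - 0.4dp) = 4 + 0.8dv - 2.4dp.
- Fast onset (60/85/100/100/100%): leavers carry (0.60 + 0.85 + 1 + 1)/4 = 0.8625. LOCF difference = 4 + 0.275dv - 0.825dp.

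| Dropout, vortioxetine / paroxetine | LOCF, gradual | LOCF, fast |
|---|---|---|
| 5% / 5% | 3.92 | 3.97 |
| 10% / 10% | 3.84 | 3.95 |
| 15% / 15% | 3.76 | 3.92 |
| 20% / 20% | 3.68 | 3.89 |
| 25% / 5% | 4.08 | 4.03 |
| 5% / 25% | 3.44 | 3.81 |
| 30% / 5% | 4.12 | 4.04 |

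With no true difference (both means -4), the LOCF error is 1.6(dv - dp) for gradual and 0.55(dv - dp) for fast onset. At 25% versus 5% that is 0.32 and 0.11.

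**4. Simulation with score-related dropout.** Assumptions: 4 arms of 88, five visits, SD 8.5, AR(1) correlation 0.75, and logistic dropout with slope 0 to 1.0 per SD of the last observed score. Center, sex and baseline are omitted. These are selected scenarios, not bounds.
- Equal dropout, 5-20%: LOCF is short by about 0.03-0.34 points, at most about a quarter of one SE (0.34/1.28 = 0.27).
- 25% versus 5%, gradual onset: LOCF 4.10 if dropout is unrelated to scores, 3.45 if strongly related. Reversed (5% versus 25%): 3.41 and 4.08. MMRM is 3.99-4.00 in all four.
- Adding fast onset and 30% versus 5%: LOCF about 3.3 to 4.4, MMRM about 3.95-4.04.
- No true difference (both means -4), vortioxetine 25% versus paroxetine 5%: LOCF about -0.5 to +0.3, MMRM about 0. Familywise error with LOCF is about 5-7%.
- Dropout driven by the unobserved next score (slope 0.7), 30% versus 10%, true 4.0: MMRM about 4.4, LOCF about 4.0.

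**5. Scale of a tipping-point analysis.** Lowering the imputed scores of a proportion d of vortioxetine leavers by a shift delta lowers the difference by d x delta. The conclusion changes at delta = (4.0 - z x SE)/d. With simulated MMRM SEs of 1.31/1.34/1.36/1.39 at 5/10/15/20% dropout, and imputation variance ignored:
- z = 2.241 (tested at 0.025): 21/10/6.3/4.4 points.
- z = 1.96 (tested at 0.05): 29/14/8.9/6.4 points.

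**The case against.** The strongest case for leaving the plan alone has three parts.

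**The alternatives are already prespecified.** MMRM and observed-case ANCOVA are both in SAP 7.9.3, so any divergence will be visible. That is true, but visibility does not settle which result governs. The alpha allocation settles it, in favor of LOCF.

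**The effect is probably small.** These are healthy volunteers with weekly visits, an early-termination assessment and daily adherence monitoring over 5 weeks. At equal dropout, LOCF errs by at most about a quarter of one SE and understates the difference. This stands, and it limits the severity. The documents give no dropout rate, however, so neither low nor balanced dropout can be taken from them.

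**MMRM can be worse.** If dropout follows unobserved scores, MMRM overstates the difference (about 4.4 for 4.0) while LOCF happens to land near the truth. This also stands. Promoting MMRM is justified only with a missing-not-at-random check beside it.

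A reader might infer that LOCF tilts the trial toward vortioxetine, or that it is safely conservative. Neither is supported: the sign depends on which arm loses more subjects, the speed of onset and how strongly scores drive dropout. Nor do the documents contradict each other on the primary method.

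**Conclusion.** The point holds as a weak analysis choice that should be changed. The confirmatory Week 5 tests use earlier scores for anyone without a usable Day 32 or later score, and the better-targeted model already in the SAP carries no alpha.

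The size is conditional on assumed dropout, onset and visit correlation: a shortfall of a few tenths of a point or less at equal dropout, and an error of either sign, up to about 0.7 points below or 0.4 above a true 4.0, in the markedly unequal scenarios tried. MMRM stays near 4.0 in these scenarios only because dropout there is missing at random.

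Two stronger readings should be resisted. Type I error is not badly inflated (about 5-7% familywise against 5%). The sample-size calculation is not wrong: its figures reproduce on the inputs stated, which simply include no dropout. The gain from the change is a Week 5 estimate that is unbiased under missing at random, not more power.

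**What to change.** Before unblinding; the blinded review in Protocol 13.1 already covers whether the planned methods are suitable.

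1. Make the two Week 5 vortioxetine-paroxetine contrasts from the existing MMRM the Holm-tested primary analysis. State that they target the on-treatment Week 5 difference under missing at random, consistent with the 7-day cutoff in SAP 7.1.3.
2. Keep ANCOVA-LOCF and observed-case ANCOVA as sensitivity analyses.
3. Add one tipping-point analysis. Lower the imputed scores of vortioxetine leavers, leave paroxetine leavers at missing at random, and extend the shift until each dose's conclusion changes at its own Holm threshold (2.24 or 1.96).
4. Carry the change through Protocol 2.0 (Statistical Considerations), 13.1.3.1 and 13.1.3.2, and SAP 7.9.3 and 7.9.4. In Protocol 2.0 (Sample Size Justification) and 13.3 and in SAP 6.0, note that the stated power assumes 88 evaluable subjects per arm with no dropout.

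**Cost.** Protocol and SAP wording, the amendment with its IRB notice, and one imputation analysis; no new data. The MMRM standard error is a few percent larger (1.31-1.40 against 1.28-1.31 in the simulations). Holm power per dose is about 0-4 points lower at equal dropout: with fast onset, 82.5 against 83.5% at 5% dropout and 78.6 against 82.2% at 20%. The gap is wider where LOCF overstates the difference.
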